#### Hypotheses to be tested:

- 1. We hypothesize that patient- (e.g., health insurance) and provider-level (e.g., patient-provider race discordance) factors are associated with cardiology referral in URM people living with HIV (PLWH) at elevated CVD risk. The primary outcome measure is visit with a cardiologist after meeting criteria for elevated CVD risk.
- 2. We hypothesize that URM PLWH who are seen by a cardiologist will have better CVD outcomes compared to those without referral. Primary outcomes are blood pressure and lipid control, and secondary outcomes are myocardial infarction, stroke, death and cardiovascular death both individually and as a composite, as a function of whether an individual at elevated CVD risk was seen by a cardiologist prior to first event.
  - a. We hypothesize that guideline-directed care including tobacco cessation counseling, cardiac testing, blood pressure and cholesterol medication management, glycemic control and appropriate use of statins mediate the relationship between cardiology referral and CVD outcomes.
- 3. Aim 3 is not driven by a pre-specified hypothesis.

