## 7 Research Design and Methods

## 7.1 Study Design

This study has two overall arms with different study designs and distinct patient populations.

### 7.1.1 Study design for Aims 1 and 2

This study will perform a retrospective electronic health record-driven study of three institutions in the STAR Clinical Research Network.

Aims 1 and 2 will be addressed by a retrospective cohort study design that does not involve enrolling patients. We will analyze patient-level and provider-level data from electronic health records (EHRs) from STAR Clinical Research Network (CRN) institutions that have been mapped to the Common Data Model (CDM). These institutions include Duke University Health System, Vanderbilt University Medical Center, Medical University of South Carolina, and Wake Forest University Health Sciences.

## 7.1.2 Study design for Aim 3

Aim 3 will be addressed by a prospective, qualitative descriptive study enrolling consented participants—patients and health care providers—across four sites to identify the contextual, patient and healthcare provider-reported barriers and facilitators for achieving optimal primary CVD prevention. This aim provides the qualitative framework to develop a contextually appropriate model to prevent CVD among URM PLWH.

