## 8 Study Procedures

## 8.1 Aims 1 and 2 Study Procedures

We will analyze patient-level and provider-level data from electronic health records (EHRs) from STAR Clinical Research Network (CRN) institutions using CDM. These institutions include Duke University Health System, Vanderbilt Universities, and Medical University of South Carolina.

We (DCRI CC) will retrospectively ask the DataMarts to query the EHR for eligible patients based on age, race, ethnicity, and HIV diagnosis to identify Black/African-American and other URM PLWH. Additional data that are already collected as part of routine medical care will be extracted by sites

from patient EHRs starting at the first clinical contact after January 1, 2010, to create a contemporary cohort with at least 5 years of longitudinal follow-up data. Longitudinal follow- up data will be collected through December 31, 2020. Data will be reviewed and or collected from patient EHR from January 1, 2010 through December 31, 2020. Patients will be included for analysis in this retrospective study at the time of the first clinical encounter during an ("eligibility period") when they meet the inclusion/exclusion criteria (listed below), with a "look back period" of 1 years prior to "enrollment" (i.e., back as far as 2010) to establish medical history and other baseline factors. These dates may be adjusted during the course of the study depending on availability of data in the various DataMarts. The overall scientific premise is depicted in Section 8.2 which shows our approach without specific dates.

DataMarts, Site PIs and Site study teams will link local EHR records with death events and cause of death prior to sending the final dataset to the DCRI CC. Sites will query and link records using National Death Index Plus, State Death records, Social Security Death Mastefile, Hospital death record and/or similar death record for causes of death including cardiovascular death, retaining protected health information needed to query these databases at the site level.

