Then, DCRI will take the query data that the sites provide to identify and further stratify data for potential cohort of patients, based on additional clinical characteristics. At the earliest clinical contact within look back period, we will identify HIV status according to ICD9/10 codes and prescription of ART. We will include individuals >18 years of age and < 99 years of age, plus will ascertain time-updated data for the following potential characteristics:

hemoglobin, creatinine (or glomerular filtration rate), age, sex, race, ethnicity, insurance status, total cholesterol, HDL cholesterol, LDL cholesterol, systolic blood pressure, prescription of anti-hypertensive medications, family history of coronary artery disease, presence of diabetes, previous diagnosis of any acute myocardial infarction, hospitalization for heart failure, acute coronary syndromes, stable or unstable angina, arterial revascularization, stroke, transient ischemic attack and peripheral arterial disease presumed to be of atherosclerotic origin determined by ICD9/10 codes. Behavioral factors are smoking status, number of clinic visits per year, length of time between clinic visits and missed appointments with specialist after referral. Data will also be ascertained on HIV viral load, CD4 count, prescription of any ART and length of time on all medications. This list captures the majority of the data related to our scientific aims and will be modified as the availability of these data are discovered.

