### 4. Analytic Query(s) Activity:

DCRI CC will develop analytic queries to be distributed to DataMart sites to execute the program and provide output with data specifications as required for analysis from the indicated Common Data Model tables.

## 8.2 Overall Study Schematic for Aims 1 and 2

Sites extract data from their EHR and other ancillary systems (e.g., NDI plus, NPI, laboratory information systems) in order to populate the CDM. The quality of the data within the CDM is assessed using a set of data curation routines, which are executed every time the data are refreshed (once per quarter). The DCRI team will develop a study-specific query to identify patients using the inclusion/exclusion criteria defined below and then retrieve the required patient-and provider-level variables from the CDM at each site. Datasets will be combined into a single study database for analysis by the statisticians.

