## 12 Data analysis & statistical considerations

#### 12.1 Analysis Plan for Aim 1

For this aim, the primary outcome variable is referral to a cardiology specialist within 6 months of baseline. This will be measured as a binary variable, with 'yes' defined if there is documented evidence that a referral is made within 6 months of becoming eligible by CVD risk score and kept within 3 months of referral, and 'no' otherwise. We will also determine the time from baseline to cardiology referral and the time until the first visit with the cardiology specialist.

We will consider a number of patient and provider factors evaluated at baseline that are potentially associated with referral to a cardiology specialist. Patient factors will include demographic factors (age, sex, race, ethnicity), level of ASCVD risk, Charlson comorbidity index, SES (e.g.; 5 digit zip code, health insurance ([yes/no]), type of health insurance (Medicare, Medicaid, private, Ryan White, etc.), and history of keeping appointments during 2 years prior to baseline. Provider factors will include primary management strategy (coprimary management defined as having both an HIV doctor and Primary Care Practitioner vs. HIV provider as primary care), and years of practice since training. Cardiologist availability will be a site-determined variable. Based on prior literature, we are specifically considering sex as a biological variable that may be related to specialty referral. 

Baseline characteristics of the cohort will be summarized overall and by referral status. We will include the patient and provider factors described above, as well as vital signs (including weight, body mass index and blood pressure), laboratory measures (particularly total and HDL cholesterol, CD4 cell count, HIV viral load), and relevant medications (ART and cardiovascular medications). We will document the patterns of HIV related CVD comorbidity in the study population, as the funding opportunity announcement specified.

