Starting with the population selected for Aim 1, we will create a sub-population by matching patients referred to a cardiology specialist (the primary outcome variable for Aim 1) to similar non-referred patients. The goal of this matching is to balance factors that may be confounders of the relationship between referral and cardiovascular outcomes. We will identify factors found to be associated with cardiology referral from Aim 1, as well as factors that are expected to be associated with outcomes such as, age, race, insurance status/type, ASCVD risk score, and comorbidity index. We will not seek to match on factors that may be associated with referral but unlikely to be directly associated with outcomes. For example, we may not want to match on cardiologist availability by site if this is only related to referral and not independently to outcomes. Variables that potentially modify the effect of referral (e.g., sex, race/ethnicity, insurance status) will be included among the matching factors. Patients will be matched within sites and year of baseline encounter.

For each patient referred to a cardiologist we will identify one non-referred patient (1:1 matching) within each site. We will match using values of the individual confounders, with an exact match on sex, race/ethnicity, insurance status/type, and to within a small caliper for continuous variables (e.g., ±5 years for age). Matched pairs will be identified using optimal matching. If this approach fails to identify an adequate number of matched pairs, then 1:1 matching will be implemented using a propensity score.

Once the matching has been implemented, the same baseline characteristics reported for Aim 1 will be summarized in the matched cohort by referral status. Metrics (e.g., standardized differences) will be reported to evaluate how well-balanced the referred and non-referred groups.

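### A cardiology visit kept outside the participating health systems and not documented locally is scored 'no' in Aim 1 and can supply an unexposed control in Aim 2

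*Combined protocol and SAP*

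**What the plan says.** Hypothesis 2 in Section 4 frames the outcomes "as a function of whether an individual at elevated CVD risk was seen by a cardiologist prior to first event". The question is therefore whether the patient was seen, wherever that happened.

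The data come from one kind of source. Section 7.1.1: "We will analyze patient-level and provider-level data from electronic health records (EHRs) from STAR Clinical Research Network (CRN) institutions". Section 8.2: "Sites extract data from their EHR and other ancillary systems (e.g., NDI plus, NPI, laboratory information systems) in order to populate the CDM". The external linkage described in Section 8.1 is for mortality: sites "link local EHR records with death events and cause of death". No claims, outside-record or patient-report source is named for cardiology visits.

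Under Section 12.1 the outcome is 'yes' where "there is documented evidence that a referral is made within 6 months of becoming eligible by CVD risk score and kept within 3 months"; the 3 months run from the referral. Every other patient is 'no', and there is no category for unknown completion. Section 12.2 uses the same variable as the Aim 2 exposure: "matching patients referred to a cardiology specialist (the primary outcome variable for Aim 1) to similar non-referred patients".

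Section 8.1 lists "missed appointments with specialist after referral" among potential characteristics, and says the list will change as data availability becomes known.

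**The concern.** The 'no' group can hold three kinds of patient: those never referred, those referred who did not attend, and those referred who attended elsewhere without a local record. The third kind received the exposure that hypothesis 2 is about.

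In Aim 1 the risk is a distorted association. Health insurance is the patient factor named as an example in hypothesis 1, a model covariate, and a subgroup of primary interest. Where a patient is sent for cardiology plausibly depends on the insurance network, although the documents do not say so. If it does, an insurance odds ratio partly measures where the visit took place. That bias can go either way, and a larger sample does not remove it.

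In Aim 2 the risk is dilution. Seen patients among the controls pull the difference toward zero, provided the misclassification is unrelated to outcome.

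The planned sensitivity analyses in Section 12.1 do not reach this. The one restricted to patients with routine in-system follow-up is aimed at drop-outs, and a patient can have regular in-system HIV care and outside cardiology. Extending the referral window from 6 to 12 months does not find a visit made elsewhere.

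**Working it through.** **Inputs from the documents.** Referral rate 20-25% (Section 12.1.1), midpoint r = 0.225. Aim 1 sample 1,200-1,500 and factor prevalence 0.33 (Section 12.1.1). Aim 2 (Section 12.2.1): 300 per group; control rates 30% for blood pressure (BP) and 45% for lipids; increases of 10 and 15 points. Two-sided 0.05.

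**Assumed, because the documents give no figure.** The share k of kept visits that were outside and undocumented: 10%, 20% or 30%, overall or differing between two insurance groups.

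**1. The plan's own Aim 2 figures.** Two-proportion test, pooled variance under the null, independent groups.

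- BP, 30% vs 40%: null SE = √(2 × 0.35 × 0.65 / 300) = 0.0389; alternative SE = √((0.21 + 0.24) / 300) = 0.0387; z = (0.10 − 1.96 × 0.0389) / 0.0387 = 0.61; power 73% (stated >70%).
- Lipids, 45% vs 60%: power 95.9% (stated >95%).

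Both reproduce.

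**2. Share of the 'no' pool that was in fact seen.** If r is the true rate, m = rk / (1 − r + rk).

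- k = 10%: 0.0225 / 0.7975 = 2.8%
- k = 20%: 0.0450 / 0.8200 = 5.5%
- k = 30%: 0.0675 / 0.8425 = 8.0%

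The 20-25% rests partly on EHR data, so it may already be a recorded rate. Then m = (r/(1 − k) − r) / (1 − r):

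- k = 10%: (0.2500 − 0.225) / 0.775 = 3.2%
- k = 30%: (0.3214 − 0.225) / 0.775 = 12.4%

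**3. Aim 2 power.** The control rate becomes p0 + m(p1 − p0), so the difference shrinks by the factor (1 − m). At 300 per group:

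| m | BP difference | BP power | Lipid difference | Lipid power |
|---|---|---|---|---|
| 0 | 10.0 points | 72.9% | 15.0 points | 95.9% |
| 2.8% | 9.7 | 70.4% | 14.6 | 94.9% |
| 5.5% | 9.5 | 67.9% | 14.2 | 93.8% |
| 8.0% | 9.2 | 65.5% | 13.8 | 92.5% |

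At m = 12.4%, the top of the alternative reading, BP power is 61% and lipid power 90%.

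**4. Aim 1 with no true insurance difference.** Both groups have a true rate of 22.5%; shares a and b of visits are outside. Recorded OR = odds[r(1 − a)] / odds[r(1 − b)].

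- 10% vs 5%: 0.2025 vs 0.2138; OR 0.2539 / 0.2719 = 0.93
- 20% vs 5%: 0.1800 vs 0.2138; OR 0.2195 / 0.2719 = 0.81
- 30% vs 10%: 0.1575 vs 0.2025; OR 0.1869 / 0.2539 = 0.74

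In the 20% vs 5% case with N = 1,200 and prevalence 0.33 (396 vs 804 patients), the test at 0.05 would reject about 27% of the time although there is no true association. Swapping the two groups gives the reciprocal, 1 / 0.81 = 1.24.

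**The case against.** The strongest reply is that the plan does not define documented evidence. An outside consultation noted in the local chart might count as a kept visit, and the list of ancillary systems in Section 8.2 is given by example only. This stands. A reader might infer that every outside visit is scored 'no'; the documents support that only for visits with no local documentation.

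Section 12.1 also plans to determine time to referral and time to first visit separately. Time to referral does not depend on where the visit took place, so a factor linked to visits but not to referrals would be a warning sign. This is a partial check. It does not reclassify anyone, and the plan does not assign it that purpose.

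Section 12.2 matches within site and exactly on insurance, so the insurance argument belongs mainly to Aim 1. In Aim 2 the expected effect is attenuation, not a false benefit, if misclassification is unrelated to outcome.

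A reader might also infer that the missed-appointment variable would separate most non-attenders from patients seen elsewhere. Nothing supports that. The variable is only a potential one, and a referral that was never scheduled leaves no missed appointment. An unknown-completion class would therefore mix failed scheduling, itself an access barrier relevant to Aim 1, with care elsewhere. For the same reason, removing the class from the primary Aim 2 control pool is debatable: it selects on post-baseline information.

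Finally, the study is openly EHR-based, and this is a general limit of such data. That is true, but neither the exposure label nor the sensitivity analyses reflect the limit.

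**Conclusion.** The concern holds for patients with a referral order whose cardiology visit took place outside the participating systems and is not documented locally. They are scored 'no' and can become Aim 2 controls, and no planned analysis corrects this.

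The documents do not give the size. With 10-30% of kept visits assumed outside, the Aim 2 loss is modest: BP power of about 70-65% and lipid power of about 95-93%. At the low end the plan's BP statement still holds. The stronger reason to act is Aim 1, where an assumed 20% vs 5% split would record a null insurance odds ratio as about 0.81, and a 10% vs 5% split as 0.93.

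A reader might take these figures to show that the stated power is wrong or that an insurance association would be false. They show neither: the stated Aim 2 power reproduces, and every outside-visit rate here is an assumption. This is an improvement worth making at low cost, not an error in the plan's arithmetic.

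**What to change.** In Sections 12.1 and 12.2:

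1. Keep the primary definition, but label it 'documented in-system cardiology visit', and state whether outside visits noted in the chart count.
2. Derive a class 'referral ordered, completion unknown': an order within 6 months, no documented kept visit and, where the data exist, no in-system missed appointment. Report its frequency by insurance type and site.
3. Aim 1 sensitivity analyses: rerun the model with this class excluded, then with it counted as 'yes'. Read the results as bounds, because the class also contains referrals that were never scheduled.
4. Aim 2 sensitivity analysis: repeat the matching with this class removed from the control pool, and note that this selects on post-baseline information.

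The cost is SAP wording, one derived category and a few reruns. Referral and visit data are already needed for the outcome rule; the missed-appointment refinement depends on availability. At a 20-25% referral rate there are 0.80/0.20 = 4 to 0.75/0.25 = 3 non-referred patients per referred patient, but matching within site and year and exactly on sex, race/ethnicity and insurance may still lose pairs in step 4. Outside visits without a referral order remain unseen.

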## 5 Background and Significance

Cardiovascular disease among PLWH disproportionately affects URM populations in the U.S., and is an NIH HIV High Priority Topic of research. Multiple cohort studies have found that HIV infection is associated with increased risk of myocardial infarction, ischemic stroke, and heart failure. The literature shows a 27-75% increased risk for CVD attributable to HIV infection. In addition, PLWH are less likely than uninfected persons to receive treatment and procedures related to CVD. Under-represented racial and ethnic populations in the Southeast "HIV-belt" and "Heart Attack belt" face the highest comorbidity from HIV and cardiovascular disease (CVD) in the nation, accounting for 43% of all new HIV infections and CVD death rates 4x greater than other regions. Despite the benefit of cardiology referral for primary prevention of CVD8, URM are the least likely to be referred to cardiologists when overt CVD exists, 10 or when patients are at high risk for CVD. 12,13. Due to historical stigma, PLWH have been reluctant to engage in medical care outside of their HIV provider. Referral

to cardiology care may benefit PLWH at elevated CVD risk, however, we lack knowledge on the determinants of specialty referral and whether referrals improve cardiovascular outcomes for URM PLWH. The field needs knowledge on the effectiveness of cardiology referrals for URM PLWH. Such evidence will ultimately inform clinical care guidelines and health system interventions to improve health for URM populations with HIV.

Thus, the long-term goal of this proposal is to generate evidence-based recommendations for the management of CVD risk in PLWH. The overall objectives of this application are to demonstrate the effect of cardiology referral on CVD outcomes in a racially/ethnically diverse cohort of PLWH, and to generate qualitative data with which to develop of a future intervention. Our central hypothesis is that cardiology referral reduces incident CVD events in URM populations with HIV compared to non-referral. Our hypothesis has been formulated based on our own work identifying that race and provider specialty impact cardiovascular risk management. The rationale for our research is that, once it is known how health disparity populations with HIV access cardiology referrals, and the impact on CVD outcomes, an intervention can be appropriately designed resulting in new and innovative approaches to the management of URM PLWH at elevated CVD risk.

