#### 7.3.2 Patient EHR data for Exclusion criteria for Aims 1 and 2:

- (1) Age <18 years of age or >99 years of age at index event;
- (2) Pre-existing ASCVD prior to index event, including a previous diagnosis of any acute myocardial infarction, heart failure, acute coronary syndromes, stable or unstable angina, arterial

revascularization (includes coronary arterial or peripheral), stroke, transient ischemic attack or peripheral arterial disease presumed to be of atherosclerotic origin determined by ICD codes;

- (3) Encounter with cardiology specialist within 1 year prior to index
- (4) Evidence of ART for pre-exposure prophylaxis (i.e., Truvada [emtricitabine/tenofovir disoproxil fumarate] or post-exposure prophylaxis (e.g., Truvada plus raltegravir) without HIV diagnosis.

## 7.4 Inclusion and exclusion criteria for Aim 3

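### Aim 2 counts any kept cardiology referral as exposure whatever its reason, and nothing named in the plan balances cardiac symptoms or new cardiac diagnoses that prompt referral: event comparisons are likely biased against referral, and the sign for blood pressure and lipid control is unknown

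*Combined protocol and SAP*

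**What the plan says.** **Exposure.** Section 12.1 defines the Aim 1 outcome as yes when "a referral is made within 6 months of becoming eligible by CVD risk score and kept within 3 months of referral". No reason for referral is required. Section 12.2 builds the Aim 2 cohort by "matching patients referred to a cardiology specialist (the primary outcome variable for Aim 1) to similar non-referred patients", so the Aim 1 outcome becomes the Aim 2 exposure.

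**Purpose.** Section 5 motivates the work by the "benefit of cardiology referral for primary prevention" of CVD, and its central hypothesis is that referral lowers incident CVD events.

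**Exclusions.** Section 7.3.2 removes "Pre-existing ASCVD prior to index event". The conditions it lists include "heart failure, acute coronary syndromes, stable or unstable angina, arterial" revascularization, stroke, TIA and peripheral arterial disease. It also removes patients with an "Encounter with cardiology specialist within 1 year prior to index". Both rules look back from index.

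**Covariates and matching.** The Aim 1 factors in section 12.1 are evaluated at baseline. Section 12.2 matches on Aim 1 predictors and on "factors that are expected to be associated with outcomes such as, age, race, insurance status/type, ASCVD risk score, and comorbidity index". Section 8.1 lists time-updated variables for extraction and allows the list to change.

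**Outcomes.** Blood pressure and lipid control are co-primary. MACE, heart failure hospitalization, coronary artery disease and death are among the secondary outcomes. Time zero is the referred patient's kept visit.

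**The concern.** A patient sent to cardiology for new chest pain, breathlessness, syncope, palpitations, an arrhythmia or a murmur counts the same as one sent for risk-factor management. The first kind of patient may already have disease that is declaring itself; a matched control will usually have no such trigger. Section 12.2 states that matching is meant to balance confounders of referral and cardiovascular outcomes. A new cardiac complaint plausibly drives both, yet it is absent from the named factors.

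At stake is the reading of the event hazard ratios: a real benefit could be hidden or reversed. The coronary disease outcome, which can be met by a diagnosis code, adds detection by cardiology work-up in the same direction. For blood pressure and lipid control, the exposed group mixes visits with different purposes, so the contrast is harder to interpret and may be diluted.

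**Working it through.** **1. The unprotected window.** Referral may occur up to 6 months after index and the visit up to 3 months after referral: 6 + 3 = 9 months. Exclusions end at index and the Aim 1 factors are measured at baseline. A symptom or diagnosis first arising in this window is covered by no stated rule. Before index, the conditions not listed are arrhythmia, valve disease, other heart disease without heart failure, and symptoms without an angina code.

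**2. Is indication captured elsewhere?**
- Section 12.1 factors (demographics, ASCVD risk, Charlson index, socioeconomic status, appointment history, management strategy, years of practice, cardiologist availability): no symptom or indication variable. Aim 1 cannot pass to Aim 2 a predictor it never tested.
- Section 8.1 list: angina, acute coronary syndromes and heart failure hospitalization are there; non-specific symptoms, arrhythmia and valve disease are not.
- Section 12.1 sensitivity analyses, carried to Aim 2 by section 12.2: none addresses the reason for referral.

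**3. The plan's own power figures.** Section 12.2.1 gives 300 per group, 30% vs 40% for blood pressure control and 45% vs 60% for lipid control (increases read as absolute points). With two-sided 0.05 and pooled variance under the null:

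power = Φ[(d − 1.96·SE0)/SE1], where SE0 = √(2p̄(1−p̄)/n) and SE1 = √((p1(1−p1)+p2(1−p2))/n)

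- Blood pressure: (0.10 − 1.96 × 0.03894)/0.03873 = 0.611, power 73.0%. Stated: above 70%.
- Lipids: (0.15 − 1.96 × 0.04077)/0.04031 = 1.739, power 95.9%. Stated: above 95%.

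Both reproduce. The point concerns validity, not a wrong figure.

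**4. Secondary events.** The documents give neither the share of referred patients with a cardiac trigger (q), nor the share of controls (s), nor the risk multiplier (m). Assume s = 5%.

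observed ratio ≈ true ratio × [1 + q(m − 1)] / [1 + s(m − 1)]

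| q | m | bias factor | true 1.00 appears as | true 0.75 appears as |
|---|---|---|---|---|
| 20% | 1.5 | 1.10/1.025 = 1.07 | 1.07 | 0.80 |
| 20% | 2 | 1.20/1.05 = 1.14 | 1.14 | 0.86 |
| 30% | 3 | 1.60/1.10 = 1.45 | 1.45 | 1.09 |

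The formula is for risks. With MACE at about 5% by 5 years (section 12.2.1), it approximates the hazard ratio. The bias runs against referral whenever q exceeds s and m exceeds 1.

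**5. Co-primary blood pressure control.** Suppose preventive referrals gain 10 points and indication-driven referrals gain e points. The average gain is (1 − q) × 10 + q × e.

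| e | q = 20%: gain, power | q = 30%: gain, power |
|---|---|---|
| 0 | 8.0, 54% | 7.0, 44% |
| 10 | 10.0, 73% | 10.0, 73% |
| 15 | 11.0, 80–81% | 11.5, 84% |

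The effect can shrink, stay or grow, so no direction follows. For lipids with e = 0, the 15-point gain falls to 12.0 (power 84%) or 10.5 (73%).

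**6. Precision of a restricted comparison.** Removing a share q from 300 per group:

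| q | n per group | blood pressure power | lipid power |
|---|---|---|---|
| 20% | 240 | 63% | 91% |
| 40% | 180 | 51% | 82% |

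**The case against.** Several parts of the plan narrow the problem. Heart failure and diagnosed angina before index are excluded, and the one-year cardiology washout removes many patients already followed for arrhythmia or valve disease. A reader might infer that non-atherosclerotic heart disease is left in altogether; section 7.3.2 does not support that. The matching list is open, it includes a comorbidity index, and the extraction list is time-updated and modifiable. Section 12.1 also allows subgroups with very common referral to be excluded in sensitivity analyses. All of this stands as partial protection. None of it names the indication, and a baseline covariate cannot balance a trigger that comes later.

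The stated aims refer to cardiology referral, or being seen by a cardiologist, without limiting it to preventive referral; the primary-prevention wording is background, and cardiac testing is among the hypothesized mediators. That also stands. The plan does not state a preventive-only estimand, so a preventive-only comparison belongs in a sensitivity analysis. Confounding by indication remains a problem for the estimand the plan does state.

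Finally, the events are secondary, and section 12.2.1 already expects only modest power for them. This limits the consequence, but a shortage of power is not the same fault as bias.

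**Conclusion.** The point holds in a limited form. Aim 2 cannot separate preventive from symptom-driven referral as written, and its secondary event comparisons are likely biased against referral. A true hazard ratio of 0.75 could appear as about 0.8 to 1.1. That range rests entirely on assumed inputs (20–30% of referred and 5% of control patients with a trigger, risk raised 1.5- to 3-fold) and shows plausible size, not an estimate.

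A reader might infer that Aim 2 as a whole is biased against referral. The documents do not support this. For co-primary blood pressure and lipid control the sign is undetermined, and requiring a kept appointment only in the referred group could favor referral by selecting adherent patients. A reader might also infer that Aim 1 omits the strongest determinant of referral; nothing in the documents ranks determinants, so only the omission can be stated.

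This is a change the sponsor should make. No stated figure is wrong.

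**What to change.** In section 12.2, derive two indicators from Common Data Model diagnosis codes: (a) cardiac symptoms (chest pain, dyspnea, syncope, palpitations); (b) arrhythmia, valve disease or cardiomyopathy. For each patient, assess them from 12 months before that patient's own index to the same elapsed time after index in both pair members, ending at the elapsed time of the referred patient's referral date. Leave out codes assigned at the cardiology visit, since these may result from the exposure. Elapsed time is needed because time zero is counted from baseline and pairs share only the baseline year, not the date.

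Add both indicators to the matching factors, or to the propensity score if exact matching loses too many pairs. Keep the full matched cohort as the main analysis, and repeat the co-primary and event analyses in pairs with neither indicator as a sensitivity analysis. In section 12.1, add both indicators, dated on or before index, as Aim 1 covariates.

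The cost is a code list and two derived variables from data already coded. Some referred patients will lose their match, and the sensitivity subset will be less precise, as step 6 of the working shows. The plan should state that loss of precision beside the result.
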